### **6.2.2 Practical Strategies to Enhance Adherence and Retention**

Although retention in one phase influences retention in another, drop-out from one phase does not necessarily imply drop-out from another; participants can be lost, resistant, or refusing additional contact and each of these types requires standardized decision rules for management. However, special attention should be paid to contacting refusing participants. Participants who state that they do not want to be contacted must not be contacted. Contacting these participants is disrespectful and may result in an IRB complaint or a complaint made to community representatives.

General guidelines to enhance adherence and retention are listed below:

- Collect some data, if possible. Prioritize primary outcome measures (e.g., Form 90, ASI)
- Be flexible in scheduling assessments on early morning and evenings. Check with participants about best days and times to come in.
- Provide local bus schedules
- Prepare waiting areas for family members that accompany participants.
- Send participants holiday and birthday cards to keep in touch and show appreciation for participant's involvement
- Offer incentives for transportation (\$25 for less than 50 miles, \$50 for > 50 miles)
- Pick participants up for follow-up interviews
- Conduct a phone interview
- Make a home visit
- Use text messaging if the participant has indicated that this is acceptable
- Conduct regular discussions among research staff as well as between research and clinical staff to clarify roles and responsibilities and to strategize about optimal ways of interacting with the specific participant
- Adopt an understanding, empathic, and respectful stance and show genuine interest in knowing why the participant wishes to drop out
- Offer a sympathetic ear to a participant who initiates a conversation about his/her life difficulties or about the lack of support they receive from their network (i.e.,

significant other, AA, friends); however, AVOID engaging in further discussion and refer the participant to the PC or PI who a) may be more experienced in this domain, and b) has less frequent interaction with the participant.

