#### **4.3.2 Addiction Severity Index - Southwest Native American Adaptation\***

A second key domain in outcome assessment is the measurement of adverse consequences of use. Our standard instrument here will be the Addiction Severity Index (ASI) Southwest Native American Adaptation, a structured interview that has been in routine use at CASAA for over a decade and that was adapted for use in this Southwest Native American tribe. The ASI evaluates severity of life problems in a variety of areas, and it has well-established psychometric characteristics (McLellan, 1985).

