If a research interview has been missed, at the next interview the Form 90 and the ASI should be completed regarding the period from the last completed interview. If the participant cannot be reached for the final follow-up interview, the RA will continue contacting the individual for 4 mos. after the scheduled follow-up date.

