### **7.5 Data Analysis Plan**

The primary dependent measure of use derived from the Form 90 and the saliva drug tests will be percent days abstinent from: alcohol, amphetamine, cannabis, cocaine, and inhalants. Secondary outcomes measures include other self-report assessments such as self-reported days of substance use and oral saliva drug results, self-efficacy, negative consequences, cultural identity, microaggressions and sexual risk behaviors. Outcome data will be analyzed using two-group MANOVA comparing MICRA and TAU conditions on key dependent measures: (1) percent days abstinent from all substances of abuse as measured from timeline follow-back, and (2) level of substance related problems as measured by the InDUC. The endpoint for this analysis will be 4-month follow-up and baseline levels of the dependent measures will be entered as covariates. Later analysis will explore outcomes across 12 months post-randomization. Secondary analyses will employ hierarchical linear modeling (HLM) for modeling effects over time given we have at least 3 time points. Exploratory analyses will also encompass outcomes on secondary measures such as ASI, cultural identity, microaggressions, brief symptom inventory, and sexual risk behaviors. Alpha level will be set at .05. The study's statistician or PI will analyze these data using SPSS software and Amos.

*Appendix A*

**SOUTHWEST NATIVE AMERICAN MICRA PROJECT  
[name]  
[name]**

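### Section 6.2.2 tells staff to prioritise the ASI as a primary outcome measure, but Section 7.5 puts the InDUC in the 4-month MANOVA and makes the ASI exploratory

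*Protocol*

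**What the plan says.** - **Section 6.2.2** (retention guidelines) deals with interviews in which only some data can be had. It instructs: "Prioritize primary outcome measures (e.g., Form 90, ASI".
- **Section 4.3.2**, which describes the ASI, says: "A second key domain in outcome assessment is the measurement of adverse consequences of use". It continues: "Our standard instrument here will be the Addiction Severity Index (ASI) Southwest Native American Adaptation".
- **Section 7.5** makes percent days abstinent the primary dependent measure. It then plans a "two-group MANOVA comparing MICRA and TAU conditions on key dependent measures", the second of which is "2) level of substance related problems as measured by the InDUC". The endpoint of that analysis is the 4-month follow-up, with baseline levels as covariates.
- **Section 7.5** places the ASI lower: "Exploratory analyses will also encompass outcomes on secondary measures such as ASI".
- **Table 6.1 (Follow-up Assessments)** schedules both the ASI and the InDUC at 4, 8 and 12 months. **Section 6.1** lets a follow-up interview run over several days, provided it is finished within a week.

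**The concern.** The research assistant decides in the field what to collect when a participant will not finish. The instruction for that moment should put first the measures that the 4-month analysis needs. The only two instruments that 6.2.2 names are Form 90 and the ASI. The MANOVA in 7.5 needs Form 90 and the InDUC.

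Two things are at stake. The first is missing data in the 4-month analysis, which a later analysis plan cannot repair because a questionnaire that was never given has no value to analyse. The second is clarity about which consequences measure was the planned one. While the sections disagree, either instrument could be presented afterwards as the intended second outcome.

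**Working it through.** No figure in the protocol has to be reproduced here. The check sets the texts side by side and follows one incomplete interview through to the analysis.

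**1. Role given to each instrument**

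| Instrument | Section 4.3.2 | Section 6.2.2 | Section 7.5 |
|---|---|---|---|
| Form 90 | not addressed | primary, prioritise | source of the primary measure, in the MANOVA |
| ASI | standard instrument for the second key domain | primary, prioritise | secondary, exploratory |
| InDUC | not mentioned | not named | second key dependent measure, in the MANOVA |

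The ASI row contains the contradiction: 6.2.2 calls it primary and 7.5 calls it secondary. Section 4.3.2 is context. It uses neither label, but it leans the same way as 6.2.2.

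**2. Does any other text settle it?** No. Table 6.1 schedules both instruments without ranking them. The descriptions of the instruments in Chapter 4 do not say which one enters the main analysis.

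**3. One incomplete 4-month interview**
- The participant attends, completes Form 90 and the ASI as 6.2.2 directs, stops, and does not return within the week.
- Percent days abstinent is available and the InDUC is not.
- A standard MANOVA needs both dependent variables, so the case is dropped and its Form 90 result goes with it.
- The 8-month visit does not restore the value. Section 6.3 sets the InDUC recall period at follow-up as the time since the last research interview, so a later InDUC is not a 4-month InDUC.

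**4. Scale per case.** Section 5.1 plans 40 per arm. One dropped case is 1/40 = 2.5% of an arm. At the 80% follow-up that Section 6.1 mentions, an arm has 0.80 × 40 = 32 participants, and one case is 1/32 = 3.1%. The document gives no basis for the number of such cases, so no total loss and no loss of precision is calculated.

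**The case against.** The case against giving this much weight has several parts.

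- **The list in 6.2.2 is open.** It gives examples, so the InDUC is not excluded, and it sets no order of administration. That is true. But an example must belong to the class it illustrates, so the ASI is still classed as primary, which 7.5 denies.
- **Section 4.3.2 is soft support.** A domain may have two instruments, with one chosen for the MANOVA. This stands, and the section is used here only as context.
- **Few interviews are exposed.** Section 6.2.3 covers participants who say they will not return and asks only for final Form 90 information, naming neither the ASI nor the InDUC. The priority rule in 6.2.2 therefore bites mainly on people who give part of an interview and do not complete it within the week. This stands and limits the effect.
- **The trial is a pilot meant to estimate effect sizes (Aim 4).** This also argues for a moderate weight, although an effect size for the InDUC still depends on the InDUC being collected.

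Three stronger readings are tempting, but the protocol does not support them.

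- A reader might infer from Section 6.2.1 that the ASI outranks the InDUC, because after a missed interview "at the next interview the Form 90 and the ASI should be completed regarding the period from the last completed interview". That sentence sets a recall period and ranks nothing. Section 6.3 gives the InDUC the same window.
- A reader might infer that 7.5 contradicts itself by listing consequences as secondary: "Secondary outcomes measures include other self-report assessments such as self-reported days of substance use and oral saliva drug results, self-efficacy, negative consequences". Section 7.5 ties that phrase to no instrument. Section 4.3.2 assigns adverse consequences to the ASI, and on that reading 7.5 is consistent on this point.
- A reader might compare the baseline times in Table 4.1 (60 minutes for the ASI, 15 for the InDUC) and treat the difference as the size of the problem. Follow-up times are not given, and minutes do not measure lost data.

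**Conclusion.** The inconsistency is real and stands in the text. Section 6.2.2 classes the ASI as a primary outcome measure, 7.5 classes it as secondary and exploratory, and the instrument that 7.5 does put in the 4-month MANOVA is not named in 6.2.2. The document does not show which side is the slip.

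The practical effect is modest and confined to interviews that stay incomplete, in unknown number. It rests on two assumptions: that staff read the two named examples as the priority set, and that the MANOVA is run in its standard form on cases with both outcomes. A method that retains partly observed cases would keep the Form 90 information, but the InDUC value would still be missing.

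It would go too far to say that the InDUC will be lost on any material scale, or that 7.5 calls the InDUC primary. It calls it a key dependent measure and reserves the word primary for percent days abstinent.

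**What to change.** Before outcomes are compared by arm, confirm which instrument is the second key measure, and make 6.2.2, 4.3.2 and 7.5 agree.

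- **If 7.5 is right as written:** change the bullet in 6.2.2 to read *Prioritize the main-analysis measures (Form 90, InDUC-2R), then ASI*. State in 4.3.2 that the InDUC is the consequences measure for the main analysis.
- **If the ASI was intended:** 7.5 must name it in place of the InDUC and specify the ASI score that serves as the dependent variable, since 4.3.2 describes an interview covering several problem areas. The ASI then leaves the exploratory list, and 6.2.2 can stand.

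The cost is a few words in up to three sections and a short briefing of the research assistant. The downside of the first option is that some exploratory ASI data may be lost in shortened interviews.

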### **6.2.3 Working with Ambivalent Research Participants**

See Table 6.1 for a list of risk factors that may be associated with non-adherence during enrollment, treatment, and follow-up. These factors may be explicitly expressed by participants or observed by the study staff.

Participants may choose to drop out for a variety of reasons. They may have the perception that they have given the same information over and over again. They may complain that the treatment is not effective because their substance use has not improved or that treatment is not warranted any more because they are able to abstain from drinking/using. Participants may also think that their contribution to the study is minimal. Some participants may have concerns about the time commitment or they may have transportation or other constraints that prevent their active participation in the study. On a general level, it is important to identify the reasons for non-adherence and to address them by allowing flexibility with the study procedures. If a participant expresses reservations about continuation of the study, the research staff should respectfully listen to these reservations and use the following techniques:

- Call participant to find out their standing regarding the study
- Explore reasons for not wanting to participate
- Inform participant that research visits can be resumed at any time
- Re-iterate number of research visits that still need to be completed
- If the participant indicates that they will not be coming back to the research visits, ask for permission to collect final Form-90 information by phone or in person
- Emphasize the participant's importance to the study regardless of drinking/using status
- Normalize the phenomenon of losing interest in the study
- Arrange a meeting between the participant and the PC and later the PI to:
  - Identify obstacles to compliance
  - Engage the participant in active problem-solving
  - Offer help with problems that may be an obstacle to compliance
- Request permission to re-contact at a later time

The art is to avoid eliciting a 'NO' response. Examples include:

“It sounds as though today is not a good day for you to complete the interview. How about I give you a call next week and see if we can find a more convenient time?”

“Thank you for your participation so far and for coming in today. I respect your wishes not to finish the interview today. Would it be okay if I called you in a few weeks just to check in?”

Another option is to thank the person for coming and not ask at that moment whether or not you can reschedule an interview. Perhaps it might be more effective to:

- Follow-up with a thank you letter and mention that the research staff will try to call them and see if they have changed their mind.
- Follow-up with a phone call only

Project Match (Monograph 7) suggests that the Research Assistant indicate that he/she does not have the authority to “dissolve the research agreement” and request that the participant speak with the PC/PI. This strategy serves several purposes:

- Emphasizes the importance of the decision and the value of the participant’s contribution to the study.
- Provides participants with another opportunity to rethink their decision.
- A person of greater authority may be able to more effectively address the concerns of the participant.

In some cases, it may be best to proceed with immediate referral to the PI. There are several reasons for immediate PI referral. First, the participant may have already spoken with the PC about the issue, or may want to speak to the PI about the PC. Second, it may be difficult to convince a refusing participant to attend two separate meetings or to speak with two different people. Given that the PI may be seen as a person with more authority, it may be more efficient to proceed with setting up a meeting/phone call with the PI. However, the preferred procedure may be site-specific. Before referring the participant to the PC/PI, the following information may facilitate a smooth hand-off:

- familiarity with the participant’s reason(s) for not wanting to participate, and
- the perception/speculation of the Research Assistant of the participant’s reasons to drop out of the study

If, despite all best efforts, the participant refuses to re-engage, accept their choice. Thank them for their participation thus far with a thank you letter signed by all members of the research team. Also, let the participant know that she/he can come back at any time, and ask if it is possible to mail study materials periodically.

**Table 6.1 Enrollment, Treatment, and Follow-up Risk Factors**

Enrollment Phase Risk Factors:	Treatment Phase Risk Factors:	Follow-Up Phase Risk Factors:

Expressed
 
 
• Concerns about randomization
 
• Expectations for being assigned a specific treatment
 
• Concerns with one or some aspects of the study protocol
 
• Other expressed enrollment risks
 
 
Observed
 
 
• Rescheduled screening appointments
 
• No-show for screening appointments
 
• BAC>0 at baseline interview
 
• Problems with detoxification
 
• Permanent address is different from current address
 
• Duration of current address is less than 3 months
 
• Plans to move in the next year
 
• Other observed enrollment risks
 
	
Expressed
 
 
• Dissatisfaction with treatment assignment
 
• Dissatisfaction with treating clinician(s)
 
• Difficulty to meet time demands
 
• Other expressed treatment risks
 
 
Observed
 
 
• Rescheduled treatment appointments
 
• No-show for treatment appointments
 
• Unresponsive to or refusing routine scheduling procedures
 
• Manifestation of clinical deterioration
 
• Early drop out from treatment
 
• Plans to move in the next year
 
• Loss of housing
 
• Unexpected social, occupational, or health event
 
• Lost contact (disconnected phone or out of minutes, undelivered mail)
 
• Other observed treatment risks
 
	
Expressed
 
 
• Dissatisfaction with services provided
 
• Dissatisfaction with treating clinician(s)
 
• Difficulty to meet time demands
 
• Other concerns expressed during follow-ups
 
 
Observed
 
 
• Loss of interest in the study due to end of treatment
 
• Clinical deterioration
 
• Plans to move in the next year
 
• Loss of housing
 
• Unexpected social, occupational, or health event
 
• Other observed follow-up risks
 

### **6.3 Follow-up Assessments**

Follow-up assessments are listed in Table 6.1. Phase I participants do not have a 12-month follow-up; because of this they will complete more questionnaires at the 8-month follow-up than the Phase II participants do. The procedures for the BAC and the oral fluid drug test are provided in Section 4.2. Descriptions of the assessments in Table 6.1 are given in Sections 4.3 and 4.4. Several questionnaires inquire about a different time period when given at follow-up than when given at baseline. These questionnaires include (period of interest at follow-up in parentheses):

Form-90 Interview (time since last research interview)

Addiction Severity Index (past 30 days and time since last research interview)

SCID (time since baseline interview)

Inventory of Drug Use Consequences-2R (time since last research interview)

\*\*Locator form from the baseline interview is pulled out and updated at each follow-up and whenever study staff has contact with the participant

All other questionnaires inquire about the same time period at each research interview.

**Table 6.1 Follow-up Assessments**

	4 Mos.	8 Mos.	12 Mos. (Phase II only)
BAC	X	X	X
Intercept Oral Fluid Drug Screen	X	X	X
RA-Administered Interview Measures			
Form 90 Interview	X	X	X
Addiction Severity Index	X	X	X
Locator Form (not in database)	Update	Update	Update
Substance Dependence Symptoms (SCID)		X - Phase I only	X
Self-Report Questionnaires			
Risk Behavior Questionnaire (RBQ)	X	X	X
Inventory of Drug Use Consequences - 2R	X	X	X
Brief Symptom Inventory 18 (BSI 18)	X	X	X
Beck Hopelessness Scale (BHS)	X	X	X
Condom Use Self-Efficacy	X	X	X
Alcohol/Drug Use: Confidence & Temptation	X	X	X

Scale of Ethnic Experience		X- Phase I only	X
Microaggressions Scale (MA)		X- Phase I only	X
Daily Spiritual Experience Scale	X	X	X

#### **6.4 Ending the Follow-up Assessment**

When all assessment instruments have been completed, the RA will provide the participant with \$50 cash as compensation (see Incentives SOP for details). The RA will enter the completed follow-up date into the Participant Enrollment log.

If follow-ups remain, the RA will record the next estimated follow-up date in the Participant Enrollment Log and provide the participant with an appointment card for that follow-up. The RA will also outline the remaining parts of the study for the participant, thank him or her for participating in the study, and emphasize how important his or her participation is.

If it is the participant's last follow-up, the RA will give the participant a Certificate of Completion and thank the participant for his or her contributions to the study. The RA will answer any final questions about the study and encourage the participant to call if he or she has any questions about the study in the future.

## Chapter 7: Data Management Procedures

### **7.1 Quality Control Procedures**

#### **7.1.1 General Instructions for Completing Forms**

Use black ballpoint pen (not pencil) for completing all interview-based forms. The first page of all of the self-administered forms contains specific instructions to the participant on how to respond to the questionnaire. An administrative area is also on the first page of each form for identification and linkage of the instrument to a particular time point.

(Note: The Locator Form does not include a place for ID # because it is stored separately from the assessment forms and contains identifying information) The administrative section should be completed before giving the questionnaire to the participant. Make no erasures and do not use correcting fluid/white out. All self-administered forms should be carefully checked once returned for incomplete corrections, stray marks, skipped items, and items with more than one response indicated.

Print all text responses legibly; do not use cursive writing. Always retain a copy of each paper form completed either by interview, or self-administered in the permanent MICRA participant file.

Record all times in 24 hour format (also called international time, e.g., 00:00 = 12 Midnight, 06:00 = 6 AM, 20:00 = 8PM, etc.).

Record all dates in month/day/year order. Prompts on the paper forms are in the format: mm/dd/yyyy.

#### **7.1.2 Missing Responses and Forms**

Do not leave responses blank on a form. Unanswered responses embedded in a question sequence that was validly skipped because the items were not applicable are not permitted. Blank responses are not automatically assumed to be “Unknown” or “No.” Be explicit in the recording and entry of data on the study forms. When information is unavailable and will never be known place equal (“=”) signs through the blank space. For example, a missing height not recorded would appear:

Height == in.

If an entire form cannot be located and the information cannot be recovered, write “Missing” on the session checklist and date and initial the note. If known, include a brief comment about why the form was not completed.

#### **7.1.3 Corrections**

Corrections should be made in the following manner:

- Cross out the original response with a single line in such a way that it is still legible.
- Write the correct response above or to the side of the original response.
- Date and initial the correct response.

For example: What is the participant's gender?    Male     Female

Do not use white out or erasures at any time.

